#### 11.2.2.4 Rate of adherence to medication of COPD patients according to the SMAQ three-months after the switch

Estimand:

A. Population: Is defined through inclusion/exclusion criteria of the study protocol to reflect the target population.

B. Variable: Binary variable response.

C. Intercurrent Event (IE): Include death, drop-out due to any adverse event (AE) and treatment discontinuation. For patients experiencing an IE, the most extreme unfavourable value will be assigned (Patient not adhered).

D. Population level summary: Proportion of adhered and not adhered patients.

For this endpoint frequency tables will be provided.

**11.2.2.5 Mean total score in abbreviated Q (first 13 questions of Part 1) (patient satisfaction with the inhaler device) approximately three-months after the switch**

Estimand:

A. Population: Is defined through inclusion/exclusion criteria of the study protocol to reflect the target population.

B. Variable: Continuous variable response.

C. Intercurrent Event (IE): Include death, drop-out due to any adverse event (AE) and treatment discontinuation. For patients experiencing an IE, the most extreme unfavourable value will be assigned (Total score equals to 13).

D. Population level summary: Mean total score of abbreviated Questionnaire three months after the switch

For this endpoint summary statistics tables will be provided.

**11.2.2.6 Mean score of overall satisfaction according to Question 14 of PASAPQ (Part 1) three-months after the switch.**

Estimand:

A. Population: Is defined through inclusion/exclusion criteria of the study protocol to reflect the target population.

B. Variable: Continuous variable response.

C. Intercurrent Event (IE): Include death, drop-out due to any adverse event (AE) and treatment discontinuation. For patients experiencing an IE, the most extreme unfavourable value will be assigned (Score of Question 14 equals to 1)

D. Population level summary: Mean score of overall satisfaction three months after the switch.

Estimand will be assessed by summary statistics.

**11.2.2.7 Proportion of preference (Spiriva® Handihaler® vs Spiolto® Respimat®) according to PASAPQ (Part 2) three-months after the switch**

Estimand:

A. Population: Is defined through inclusion/exclusion criteria of the study protocol to reflect the target population.

B. Variable: Binary variable response.

C. Intercurrent Event (IE): Include death, drop-out due to any adverse event (AE) and treatment discontinuation. For patients experiencing an IE, the most extreme unfavourable value will be assigned (Preference of Spiriva Handihaler®)

D. Population level summary: Proportion of patients preferring Spiriva® Handihaler® and proportion of preferring Spiolto® Respimat®.

Estimand will be assessed by summary statistics.

11.2.2.8 Mean score of willingness to continue with inhaler (Spiolto® Respimat®) according to PASAPQ (Part 2) three-months after the switch.

Estimand:

A. Population: Is defined through inclusion/exclusion criteria of the study protocol to reflect the target population.

B. Variable: Continuous variable response.

C. Intercurrent Event (IE): Include death, drop-out due to any adverse event (AE) and treatment discontinuation. For patients experiencing an IE, the most extreme unfavourable value will be assigned (Willingness to continue equals to 0)

D. Population level summary: Mean score of willingness to continue with the inhaler Spiolto® Respimat®.

Estimand will be assessed by summary statistics.

11.2.2.9 Mean change of patients' dyspnea status according to the mMRC scale within three-months after the switch.

Estimand:

A. Population: Is defined through inclusion/exclusion criteria of the study protocol to reflect the target population.

B. Variable: Continuous variable response.

C. Intercurrent Event (IE): Include death, drop-out due to any adverse event (AE) and treatment discontinuation. For patients experiencing an IE, the most extreme unfavourable value will be assigned (Dyspnea status equals to 4)

D. Population level summary: Mean change of Baseline of Dyspnea status within 3 months

This endpoint will be analysed with a Mixed Model for Repeated Measures (MMRM) with mMRC score as dependent variable. Visit, GOLD group, smoking habits, packyears, sex, age, and comorbidities appearing at a rate greater than 5% will be entered as covariates. Patients will be fitted at random and an unstructured covariance matrix will be used, allowing adjustment for correlations between study visits within the study patients. The Kenward- Roger degrees of freedom approximation will be used in the model (ddfm=kr).

Summaries of the estimated mean change from baseline of mMRC at 3 Months will be provided with 95% confidence interval. Model information will be provided as footnote under the corresponding table

### 11.2.3 COVID-19 IMPACT

The COVID-19 pandemic started before first patient first visit; it is necessary to analyse the possible impact of the pandemic to this NIS. Separated tables will capture the number of patients dropped-out due to COVID-19, the frequencies of deaths, AEs and SAEs related to COVID-19 and the number of visits delayed/not done due to the pandemic.

**11.4 Safety Analysis**

All safety analyses will be performed on TS.

**11.4.1 Adverse events**

All treatment emergent adverse events recorded during the trial will be presented in listings for AEs / SAEs. Especially the Adverse Drug Reactions (ADR), these might be followed up after the study completion and until they are resolved. As treatment emergent adverse events are considered all the AEs following ICF signature providing the patient has already received treatment with Spiolto® Respimat®. Initially, an AE overview table will be created summarizing the total number of AEs, patients with at least one: AE, SAE, SAE leading to death, SAE leading to drug discontinuation and the number of pregnant patients with at least one AE. A separate table showing the overview of AE occurred during the study will be presented by SOC and PT. SOC terms will be sorted alphabetically; PTs will be sorted within each SOC term by decreasing frequency. In such tables if a patient reported more than one AE within the same PT or SOC, the patient will be counted only once for this PT/SOC. AEs will be coded based on the MedDRA terminology. The existing version at the time of the database lock will be used.

## 12. QUALITY CONTROL

To improve and secure data quality, automatic data checks upon data entry will be done within the eCRF. In the eCRF, plausible ranges of values for numeric data entries as well as logical data entries and listings will be provided for each entry field. Based on this, checks on completeness and plausibility will be performed upon data entry in the eCRF.

Validity of data entry thus is ensured by integrated validation checks performed by the system, indicating missing or implausible entries to the document list or investigator. All corrections will be visible from the systems audit trail.

No regular source data verification is planned in this study. However, in case of decreasing compliance (i.e. of missing data, data discrepancies, protocol violations, etc.) a for-cause audit or risk-based monitoring visit will be performed.

## 13. REFERENCES

### 13.1 PUBLISHED REFERENCES

### 13.2 UNPUBLISHED REFERENCES

## ANNEX 1. ADDITIONAL INFORMATION

**TABLE 1.1 DISPOSITION OF PATIENTS**

	N	%
Subjects entered the study		
Subjects discontinued		
Discontinuation reasons		
Treatment Discontinuation for any reason		
Patients decision/ICF withdrawal		
Patient is lost to follow-up		
Non-compliance to study requirements (exclusion criterion is met)		
Protocol violation		
Treatment with Spiolto Respimat discontinuation		
Adverse Event		
Investigators decision		
Other Cause		

**TABLE 1.2 PREMATURE DISCONTINUATION FROM STUDY DUE TO COVID-19**

[figure not shown]
	N	%
Subjects entered the study		
Subjects discontinued due to COVID-19		
Subjects Treated		
Prematurely discontinued from study		
AE SARS-CoV-2 infection		
COVID-19 related, not due to AE		

**TABLE 1.3 NUMBER OF VISITS DELAYED/NOT DONE DUE TO COVID-19**

	N	%
Visits completed on time		
Visits delayed due to COVID-19		
Visits not done due to COVID-19		

**TABLE 1.4 ANALYSIS SETS**

	N	%
Enrolled Set (ES)		
Treated Set (TS)		
Per Protocol Set (PPS)		

---

N=xxx

---

Gender n (%)

Male

Female

Missing

Occupation n (%)

Employee

Manager

Part timer

Self Employed

Public Service

Student

Without Occupation

Other

Missing

Education n (%)

Less than high school diploma

High school degree or equivalent

Bachelor's degree

Master's degree

Doctorate

Other

Missing

Marital Status n (%)

Single

Married

Divorced

Widow

Missing

Weight (kg)

n

Mean

Median

SD

Minimum

Maximum

Q1

Q3

Missing

Height (cm)

---

---

---

N=xxx

---

n

Mean

Median

SD

Minimum

Maximum

Q1

Q3

Missing

BMI (kg/m^2)

n

Mean

Median

SD

Minimum

Maximum

Q1

Q3

Missing

Obesity (BMI>30kg/m^2)

Yes

No

Missing

Smoking status

Never

Past

Current

Unknown

Missing

Pack years for Past and Current smokers

n

Mean

Median

SD

Minimum

Maximum

Q1

Q3

Missing

---

**TABLE 2.2 COPD HISTORY AND CLINICAL CHARACTERISTICS**

	Baseline N=xxx	3 Months N=xxx
Months since COPD diagnosis		
n		
Mean		
Median		
SD		
Minimum		
Maximum		
Q1		
Q3		
Missing		
COPD type n (%)		
Chronic bronchitis		
Emphysema		
Other COPD		
Presence of Eosinophilia in the peripheral blood n (%)		
Yes		
No		
Missing		

**TABLE 2.2.1 COPD HISTORY AND CLINICAL CHARACTERISTICS**

	12 months before baseline N=xxx	Baseline to 3 months N=xxx
Number of exacerbations n (%)		
None		
1		
2		
>2		
Missing		
Number of hospitalisations due to COPD exacerbations n (%)		
None		
1		
2		
>2		
Missing		

**TABLE 2.3 PFT MEASUREMENTS BY VISIT.**

	Baseline	3 Months
001-MCS-90-118_RD-20 (1.0) / Saved on: 25 Nov 2019		

	N=xxx	N=xxx
PFT performed		
Yes		
No		
Unknown		
Missing		
Time since PFTs performed		
n		
Mean		
Median		
SD		
Minimum		
Maximum		
Q1		
Q3		
Missing		

**TABLE 3.1 SUMMARY TABLE OF COMORBIDITIES**

	n	%
Presence of at least 1 comorbidity		
Yes		
No		
Missing		
Diabetes mellitus		
Yes		
No		
Not evaluated		
Osteoporosis		
Yes		
No		
Not evaluated		
Cardiovascular diseases (including heart failure, atrial fibrillation and other arrhythmias)		
Yes		
No		
Not evaluated		
Malignancies		
Yes		
No		
Not evaluated		

	n	%
Anxiety/Depression		
Yes		
No		
Not evaluated		
Insomnia		
Yes		
No		
Not evaluated		
Pulmonary artery hypertension		
Yes		
No		
Not evaluated		
Sleep apnoea		
Yes		
No		
Not evaluated		
Gastroesophageal reflux disease		
Yes		
No		
Not evaluated		
Hemolytic anemia		
Yes		
No		
Not evaluated		
Atopy		
Yes		
No		
Not evaluated		
Sinusitis		
Yes		
No		
Not evaluated		
Emphysema		
Yes		
No		
Not evaluated		

**TABLE 4.1 CURRENT COPD TREATMENT\*.**

	n	%
Any Short acting <math>\beta</math>2-agonists		
Salbutamol		
Terbutaline sulfate		
Any Long acting <math>\beta</math>2-agonists		
Salmeterol		
Fumaric formoterol		
Vilanterol		
Olodaterol		
Indacaterol		
Any Short-acting anticholinergics		
Bromide ipartropium		
Any Long-acting anticholinergics (LAMA)		
Bromide tiotropium		
Bromide aclidine		
Bromide glucuronide		
Bromide umecline		
Any Inhaled corticosteroids (ICS)		
Fluticasone propionate		
Voudessonide		
Furometic mometazone		
Siklesonide		
Any PDE 4 inhibitors		
Roflumilast		
Any Methylxathines		
Aminophyline		
Theophyline		
Any LABA/ICS Combinations		
Salmeterol-Fluticazone		
Formoterol-Budesonide		
Βιλαντερόλη-Fluticazone		
Formoterol-Beclomethazone		
Formoterol-Budesonide		
Formoterol-Fluticazone		
Any LAMA/LABA Combinations		
Aclidine-Formoterol		
Glycopyrronium-Indacaterol		
Tiotropium-Olodaterol		
Umeclidine-Vilanterol		

\*one year before enrolment

**TABLE 4.2 PAST COPD TREATMENT\*.**

	n	%
Any Short acting <math>\beta</math>2-agonists		
Salbutamol		
Terbutaline sulfate		
Any Long acting <math>\beta</math>2-agonists		
Salmeterol		
Fumaric formoterol		
Vilanterol		
Olodaterol		
Indacaterol		
Any Short-acting anticholinergics		
Bromide ipartropium		
Any Long-acting anticholinergics (LAMA)		
Bromide tiotropium		
Bromide aclidine		
Bromide glucuronide		
Bromide umecline		
Any Inhaled corticosteroids (ICS)		
Fluticasone propionate		
Voudessonide		
Furometic mometazone		
Siklesonide		
Any PDE 4 inhibitors		
Roflumilast		
Any Methylxathines		
Aminophyline		
Theophyline		
Any LABA/ICS Combinations		
Salmeterol-Fluticazone		
Formoterol-Budesonide		
Βιλαντερόλη-Fluticazone		
Formoterol-Becломethazone		
Formoterol-Budesonide		
Formoterol-Fluticazone		
Any LAMA/LABA Combinations		
Acclidine-Formoterol		
Glycopyrronium-Indacaterol		

	n	%
Tiotropium-Olodaterol		
Umeclidine-Vilanterol		

**TABLE 6.1.1 SUMMARY OF CAT TOTAL SCORE DURING THE TRIAL BASED ON OBSERVED DATA.**

Visit	n	Mean	Median	SD	Min	Max	Q1	Q3	Missing
Baseline	Base								
Month 3	Base								
	Post								
	Change								

Footnote: at 3 months only subjects with both baseline and post baseline value will be included.

Footnote: CAT: COPD Assessment Test.

**TABLE 6.1.2 SUMMARY OF CAT TOTAL SCORE DURING THE TRIAL BASED ON [REDACTED]**

**TABLE 6.1.3 SUMMARY OF CAT TOTAL SCORE DURING THE TRIAL BASED ON [REDACTED]**

**TABLE 6.1.4 SUMMARY OF CAT TOTAL SCORE DURING THE TRIAL BASED ON [REDACTED]**

Same shells as Table 6.1.1

**TABLE 6.2.1 CHANGE FROM BASELINE TOTAL CAT SCORE ESTIMATES DURING THE TRIAL BASED ON [REDACTED]**

Visit	LS Mean	95%CI
Month 3 Change from Baseline		
Covariate 1...n		

Footnote: CAT: COPD Assessment Test. LS: Least Square

Footnote: adjusted for covariates

**TABLE 6.2.2 CHANGE FROM BASELINE TOTAL CAT SCORE ESTIMATES DURING THE TRIAL BASED ON [REDACTED]**

**TABLE 6.2.3 CHANGE FROM BASELINE TOTAL CAT SCORE ESTIMATES DURING THE TRIAL BASED ON [REDACTED]**

Same shell as Table 6.2.1

**TABLE 7.1.1 SHIFT CHANGES OF IMPAIRED HEALTH PATIENTS BASED ON OBSERVED DATA**

CAT Score	Baseline		3 Months						Total	
	>10		<10		Missing		n	%		
	n	%	n	%	n	%				
>10										
<10										
Missing										
Total										

**TABLE 7.1.2 SHIFT CHANGES OF IMPAIRED HEALTH PATIENTS BASED ON****TABLE 7.1.3 SHIFT CHANGES OF IMPAIRED HEALTH PATIENTS BASED ON**

Same shells as Table 7.1.1

**TABLE 7.2.1 CHANGE FROM BASELINE OF THE IMPAIRED HEALTH PATIENTS DURING THE TRIAL BASED ON**

Visit	OR	95%CI for OR
Month 3 Change from Baseline		
Covariate 1...n		

Footnote: CAT: COPD Assessment Test. OR: Odds Ratio

Footnote: adjusted for covariates

**TABLE 7.2.2 CHANGE FROM BASELINE OF THE IMPAIRED HEALTH PATIENTS DURING THE TRIAL BASED ON****TABLE 8.1.1 MEAN EQ VISUAL ANALOGUE SCALE BY VISIT BASED ON OBSERVED DATA.**

Visit	n	Mean	Median	SD	Min	Max	Q1	Q3	Missing
Baseline	Base								
Month 3	Base								
Post									
Change									

Footnote1: at 3 months only subjects with both baseline and post baseline value will be included.

Footnote2: EQ-VAS's range is 0-100 where zero represents the worst state the patient can imagine and 100 the best.

**TABLE 8.1.2 MEAN EQ VISUAL ANALOGUE SCALE BY VISIT BASED ON [REDACTED]****TABLE 8.1.3 MEAN EQ VISUAL ANALOGUE SCALE BY VISIT BASED ON [REDACTED]**

Same shell as Table 8.1.1

**TABLE 8.2.1 MEAN CHANGE FROM BASELINE OF EQ-VAS BASED ON [REDACTED]**

Visit	LS Mean	95%CI
Month 3		
EQ-VAS		

\*EQ-VAS: EQ visual analogue scale.

Footnote: adjusted for covariates

**TABLE 8.2.2 MEAN CHANGE FROM BASELINE OF EQ-VAS BASED ON [REDACTED]****TABLE 9.1.1 SHIFT CHANGES OF MOBILITY DIMENSION OF EQ-5D-5L BASED ON OBSERVED DATA**

Mobility Statements	Baseline N=xxx		3 Months N=xxx									
			I have no problems in walking about		I have some problems in walking about		I am confined to bed		Missing		Total	
	n	%	n	%	n	%	n	%	n	%	n	%
I have no problems in walking about												
I have some problems in walking about												
I am confined to bed												
Missing												
Total												

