The measurement properties and responsiveness of the instrument were very similar to those of the more complex and longer St George's Respiratory Questionnaire (SGRQ). Further research has supported these findings and established the CAT as a valuable measure of health status in research ([9,10,19–21](#)). Following extensive translation and linguistic validation, the measurement properties and responsiveness of the CAT have been evaluated in many different countries and found to be similar ([9,10,19–21](#)).

Range of CAT scores from 0–40. Higher scores denote a more severe impact of COPD on a patient's life. The difference between stable and exacerbation patients was five units. No target score represents the best achievable outcome, however, CAT scores <10 corresponding to mild impact on patients life are usually considered those representing patients without impaired health status ([21,22](#)).

- **EQ-5D-5L questionnaire (23,24)** (see [ANNEX 3](#))

The EQ-5D-5L questionnaire is a well-established and commonly used tool for the measurement of a patients QoL. The EQ-5D-5L essentially consists of two parts: the EQ-

5D descriptive system and the EQ visual analogue scale (EQ VAS). The questionnaire was translated and validated for more than 170 languages.

The EQ-5D-5L descriptive system comprises five dimensions (mobility, self-care, usual activities, pain/discomfort and anxiety/depression). Each dimension has three levels (no problems, some problems, and extreme problems) and was self-reported by the patient. The patient's decision results into a 1-digit number that expresses the level selected for that dimension.

The EQ VAS records the patient's self-rated health on a vertical visual analogue scale where the endpoints are labelled 'best imaginable health state' and 'worst imaginable health state'. The VAS can be used as a quantitative measure of health outcome that reflects the patient's own judgement.

- ***Simplified medication adherence questionnaire (SMAQ)*** ([25](#)) (see [ANNEX 3](#))

This tool is a short and simple questionnaire based on questions posed directly to the patient regarding his/her medication-taking habits, which was originally validated for the measurement of adherence in patients on anti-retroviral treatment ([25](#)). The SMAQ has been extensively used for evaluating compliance with treatment for different chronic conditions.

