ANNEX 3. ADDITIONAL INFORMATION

COPD Assessment Test (CAT) (9)

Your name:	Today's date:
------------	---------------

How is your COPD? Take the COPD Assessment Test™ (CAT)

This questionnaire will help you and your healthcare professional measure the impact COPD (Chronic Obstructive Pulmonary Disease) is having on your wellbeing and daily life. Your answers, and test score, can be used by you and your healthcare professional to help improve the management of your COPD and get the greatest benefit from treatment.

For each item below, place a mark (X) in the box that best describes you currently. Be sure to only select one response for each question.

Example: I am very happy 0 1 2 3 4 5 I am very sad

						SCORE				
I never cough			0	1	2	3	4	5	I cough all the time	
I have no phlegm (mucus) in my chest at all			0	1	2	3	4	5	My chest is completely full of phlegm (mucus)	
My chest does not feel tight at all			0	1	2	3	4	5	My chest feels very tight	
When I walk up a hill or one flight of stairs I am not breathless			0	1	2	3	4	5	When I walk up a hill or one flight of stairs I am very breathless	
I am not limited doing any activities at home			0	1	2	3	4	5	I am very limited doing activities at home	
I am confident leaving my home despite my lung condition			0	1	2	3	4	5	I am not at all confident leaving my home because of my lung condition	
I sleep soundly			0	1	2	3	4	5	I don't sleep soundly because of my lung condition	
I have lots of energy			0	1	2	3	4	5	I have no energy at all	
TOTAL SCORE 										

EQ-5D-5L questionnaire (23,24)

Under each heading, please tick the ONE box that best describes your health TODAY.

MOBILITY

- I have no problems in walking about
I have slight problems in walking about
I have moderate problems in walking about
I have severe problems in walking about
I am unable to walk about

SELF-CARE

- I have no problems washing or dressing myself
I have slight problems washing or dressing myself
I have moderate problems washing or dressing myself
I have severe problems washing or dressing myself
I am unable to wash or dress myself

USUAL ACTIVITIES (e.g. work, study, housework, family or leisure activities)

- I have no problems doing my usual activities
I have slight problems doing my usual activities

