I have moderate problems doing my usual activities
I have severe problems doing my usual activities
I am unable to do my usual activities

PAIN / DISCOMFORT

[figure not shown]
- I have no pain or discomfort
I have slight pain or discomfort
I have moderate pain or discomfort
I have severe pain or discomfort
I have extreme pain or discomfort

ANXIETY / DEPRESSION

- I am not anxious or depressed
I am slightly anxious or depressed
I am moderately anxious or depressed
I am severely anxious or depressed
I am extremely anxious or depressed

- We would like to know how good or bad your health is TODAY.
- This scale is numbered from 0 to 100.
- 100 means the best health you can imagine.
0 means the worst health you can imagine.
- Mark an X on the scale to indicate how your health is TODAY.
- Now, please write the number you marked on the scale in the box below.

YOUR HEALTH TODAY =

Simplified Medication Adherence Questionnaire (SMAQ) (25)

-
1. Do you ever forget to take the medication? Yes...No
-
2. Do you always take the medication at the specified time? Yes....No
-
3. Do you ever stop taking the medication if you feel ill? Yes....No
-
4. Did you forget to take the medication during the weekend? Yes....No
-
5. In the last week, How many times did you not take a dose?
- A: None of the above
B: 1-2
C: 3-5
D: 6-10
E: Greater than 10
-
6. Since the last medical visit, how many full days did you not take the medication? Number of days:
-

Modified Medical Research Council (mMRC) questionnaire ([26](#))

Please circle the number which best describes your grade of breathlessness:

I only get breathless with strenuous exercise. 0

I get short of breath when hurrying on level ground or walking up a slight hill. 1

On level ground, I walk slower than people of the same age because of breathlessness, or have to stop for breath when walking at my own pace. 2

I stop for breath after walking about 100 yards or after a few minutes on level ground. 3

I am too breathless to leave the house or I am breathless when dressing. 4

Patient satisfaction and preference questionnaire (PASAPQ) (29)

**PATIENT SATISFACTION
AND PREFERENCE QUESTIONNAIRE**

PASAPQ

Direct version

PART 1: RATING OF SATISFACTION WITH INHALER ATTRIBUTES

Instructions: For the following questions, please check the response that best describes how satisfied you are with each of the following items. Please take as much time as you need to answer each question.

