***Relevant concomitant medications at baseline and changes up to 3-months visit:***

- Use of concomitant inhalers (Yes, No)
- Other concomitant medications

[REDACTED]

***COPD Assessment Test (CAT):*** patient-completed questionnaire assessing globally the impact of COPD (cough, sputum, dysnea, chest tightness) on health status. It is a unidimensional score based on 8 items each of them scaling from 0 to 5. Range of CAT scores from 0–40. Higher scores denote a more severe impact of COPD on a patient's life. The difference between stable and exacerbation patients is five units. No target score represents the best achievable outcome, however, CAT scores <10 corresponding to mild impact on patient's life are usually considered those representing patients without impaired health status

**EQ-5D-5L questionnaire**: a well-established and commonly used tool for the measurement of patients QoL. The EQ-5D-5L consists of two parts: the EQ-5D descriptive system and the EQ visual analogue scale (EQ VAS). The EQ-5D-5L descriptive system comprises five dimensions (mobility, self-care, usual activities, pain/discomfort and anxiety/depression). Each dimension has five levels (no problems, slight problems, moderate problems, severe problems and extreme problems) was self-reported by the patient. The patient's decision results into a 1-digit number that expresses the level selected for that dimension. The digits for the five dimensions can be combined into a 5-digit number that describes the patient's health state. The EQ VAS records the patient's self-rated health on a vertical visual analogue scale where the endpoints are labelled 'best imaginable health state' and 'worst imaginable health state'. The VAS can be used as a quantitative measure of health outcome that reflects the patient's own judgement.

**Simplified medication adherence questionnaire (SMAQ)**: a short and simple questionnaire based on questions posed directly to the patient regarding his/her medication-taking habits, which was originally validated for the measurement of adherence in patients on anti-retroviral treatment. The aim is to assess whether the patient adopts correct attitudes in relation to the treatment for his disease. It is assumed that if the attitudes are incorrect, the patient is not compliant. It has the advantage that it provides information about the causes of non-compliance. The patient is considered as compliant if all questions are answered correctly.

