**TABLE 9.5.2 SHIFT CHANGES OF ANXIETY/DISPERSION DIMENSION OF EQ-5D-5L BASED ON [REDACTED]**

**TABLE 9.5.3 SHIFT CHANGES OF ANXIETY/DISPERSION DIMENSION OF EQ-5D-5L BASED ON [REDACTED]**

Same shells as 9.1.1

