**TABLE 9.6.1.1 CHANGE FROM BASELINE ON THE MOBILITY DIMENSION DURING THE TRIAL BASED ON [REDACTED]**

Visit	OR of improvement	95%CI for OR
Month 3		
Covariate 1...n		

Footnote: adjusted for covariates OR: Odds Ratio

**TABLE 9.6.1.2 CHANGE FROM BASELINE ON THE MOBILITY DIMENSION  
DURING THE TRIAL BASED ON [REDACTED]**

**TABLE 9.6.2.1 CHANGE FROM BASELINE ON THE SELF-CARE DIMENSION  
DURING THE TRIAL BASED ON [REDACTED]**

**TABLE 9.6.2.2 CHANGE FROM BASELINE ON THE SELF-CARE DIMENSION  
DURING THE TRIAL BASED ON [REDACTED]**

**TABLE 9.6.3.1 CHANGE FROM BASELINE ON THE USUAL ACTIVITIES  
DIMENSION DURING THE TRIAL BASED ON [REDACTED]**

**TABLE 9.6.3.2 CHANGE FROM BASELINE ON THE USUAL ACTIVITIES  
DIMENSION DURING THE TRIAL BASED ON [REDACTED]**

**TABLE 9.6.4.1 CHANGE FROM BASELINE ON THE PAIN/DISCOMFORT  
DIMENSION DURING THE TRIAL BASED ON [REDACTED]**

**TABLE 9.6.4.2 CHANGE FROM BASELINE ON THE PAIN/DISCOMFORT  
DIMENSION DURING THE TRIAL BASED ON [REDACTED]**

**TABLE 9.6.5.1 CHANGE FROM BASELINE ON THE ANXIETY/DEPRESSION  
DIMENSION DURING THE TRIAL BASED ON [REDACTED]**

**TABLE 9.6.5.2 CHANGE FROM BASELINE ON THE ANXIETY/DEPRESSION  
DIMENSION DURING THE TRIAL BASED ON [REDACTED]**

Same shells as 9.6.1.1

**TABLE 10.1.1 SUMMARIES OF SMAQ QUESTIONNAIRE BASED ON OBSERVED  
DATA.**

N=xxx

Forget to take the medication for IPF

Yes

No

Missing

Always take your medication for IPF at the indicated time.

Yes

No

Missing

If feel worse, do you stop taking the medication for IPF?

Yes

No

Missing

At the last week, How often did you miss the medication for IPF?

Never

1-2 times

3-5 times

6-10 times

More than 10 times

At the past 3 Months

N=xxx

Days of missed medication for IPF

n  
 Mean  
 Median  
 SD  
 Minimum  
 Maximum  
 Q1  
 Q3  
 Missing

Days of missed one of the two daily doses of medication for IPF

n  
 Mean  
 Median  
 SD  
 Minimum  
 Maximum  
 Q1  
 Q3  
 Missing

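### The EQ-5D-5L shift-table shell has three levels for a five-level form, and the SMAQ item shell omits one item and adds one that was not asked

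*SAP*

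**What the plan says.** **EQ-5D-5L.** The form in Protocol Annex 3 offers five statements per dimension. For mobility the second is "I have slight problems in walking about" and the fifth is "I am unable to walk about". SAP section 8 agrees: "Each dimension has five levels (no problems, slight problems, moderate problems, severe problems and extreme problems". Protocol 9.3.1 does not: "Each dimension has three levels (no problems, some problems, and extreme problems". In SAP Annex 1, the rows and columns of Table 9.1.1 are no problems, some problems and "I am confined to bed", plus missing and total. The note after Table 9.5.3, "Same shells as 9.1.1", carries this layout to Tables 9.1.2 to 9.5.3, that is, to all five dimensions. SAP 8.2.2 lists the proportion of patients who improve or worsen in each dimension as a secondary outcome. SAP 11.2.2.3 analyses it with an ordinal logistic GEE and summarises it as an odds ratio.

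**SMAQ.** Protocol Annex 3 has six items, and the fourth is "Did you forget to take the medication during the weekend". Under SAP section 8, one non-adherent answer to any of the six, including a yes to item 4, makes the patient non-adherent. The item shell, SAP Table 10.1.1, refers throughout to medication for IPF. It contains the row "Days of missed one of the two daily doses of medication for IPF" and has no weekend row.

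**The concern.** Two of the shell's three EQ-5D levels are not responses on the administered form, and four of the form's five responses have no row of their own. A programmer must either invent a mapping or depart from the shell. If a mapping is invented, a patient who moves from moderate to slight, for example, may fall on the diagonal and be counted as unchanged. The shift tables are the only visible shells from which the proportions improving and worsening can be read, because Tables 9.6.x give odds ratios. A named secondary outcome would be understated in both directions and in all five dimensions.

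In the SMAQ table, a patient who is non-adherent only because of the weekend item looks adherent on every row shown. The item table and the adherence table would then disagree with no visible reason.

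**Working it through.** The documents give no figure for shifts lost, so there is none to reproduce. The check has three parts.

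**1. What any ordered collapse hides**

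Five levels give 5 × 4 = 20 shift types, of which 8 are one-level (4 up, 4 down). Collapse them into three adjacent groups of sizes s1, s2, s3 that sum to 5.

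- Hidden shift types = Σ s(s − 1). Sizes 3, 1, 1 give 6 of 20 (30%). Sizes 2, 2, 1 give 2 + 2 = 4 of 20 (20%). No other sizes are possible.
- Hidden one-level shift types = 2 × Σ(s − 1) = 2 × (5 − 3) = 4 of 8, whichever of the six ordered collapses is used.
- A five-level shell hides 0 of 20.

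These counts need no data, but they weight every shift type equally.

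**2. What share of patients' changes is hidden**

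This needs a baseline distribution and a pattern of change, and the documents give neither. All inputs here are assumptions.

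*Worked example.* Take baseline shares of 25/30/28/13/4%. Of those who can move, 25% improve one level and 8% worsen one level.

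- True improved: 0.25 × (0.30 + 0.28 + 0.13 + 0.04) = 18.75%.
- True worsened: 0.08 × (0.25 + 0.30 + 0.28 + 0.13) = 7.68%.
- Levels 2 to 4 merged. Hidden improvements: 0.25 × (0.28 + 0.13) = 10.25%. Hidden worsenings: 0.08 × (0.30 + 0.28) = 4.64%. Share lost: 14.89 / 26.43 = 56%.
- Levels 2 and 3 merged, and 4 and 5 merged. Hidden improvements: 0.25 × (0.28 + 0.04) = 8.00%. Hidden worsenings: 0.08 × (0.30 + 0.13) = 3.44%. Share lost: 11.44 / 26.43 = 43%.

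Across five assumed baseline distributions, with and without two-level improvements, the loss was 27% to 64% with levels 2 to 4 merged and 21% to 50% with the other collapse.

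*Second model.* A latent bivariate normal, with within-patient correlation 0.6 to 0.75 and an improvement of 0.1 to 0.25 SD, gives:

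| Assumed baseline shares (%) | Lost, levels 2–4 merged | Lost, levels 2–3 and 4–5 merged |
|---|---|---|
| 60/25/10/4/1 | 25–34% | 17–23% |
| 30/30/25/12/3 | 45–52% | 28–35% |
| 15/30/30/20/5 | 59–64% | 34–40% |

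Together the two models span roughly 17% to 65%. The baseline distribution and the choice of collapse drive the result, while correlation and size of shift matter less.

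**3. SMAQ items against shell rows**

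| Protocol Annex 3 item | Row in SAP Table 10.1.1 |
|---|---|
| 1 Forgetting | yes, worded for IPF |
| 2 Specified time | yes, worded for IPF |
| 3 Stopping when ill | yes, worded for IPF |
| 4 Weekend | none |
| 5 Missed doses, last week | yes, worded for IPF |
| 6 Full days missed | yes, worded for IPF |
| not asked | one of two daily doses missed |

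Five of six items have a row, and one row has no item. SAP 8.1 describes the product as taken once daily, which the extra row does not match.

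**The case against.** The strongest reply is that a literal collapse is unlikely. SAP section 8 defines five levels, section 11.2.2.3 treats the response as ordinal, and the table titles say EQ-5D-5L. A confined-to-bed label cannot serve for pain or anxiety, so the reuse note already forces the analyst to substitute wording. The mismatch should surface at programming. In addition, SAP 11.2 promises summary statistics for all primary and secondary endpoints, and section 11.3 is not visible, so another display cannot be ruled out.

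Much of this stands. The understatement is conditional on the shell being followed, and the claim must be limited to there being no other visible shell. The objection does not remove the contradiction, however. The SAP states no mapping, and a shell exists so that the programmer need not improvise. Protocol 9.3.1 also points towards three levels.

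A reader might go further and infer that about half of all EQ-5D changes would be lost. Half is exact only for one-level shift types counted equally. As a share of patients it depends on a collapse rule and distributions that the documents do not give. A reader might also infer that data are lost or that the adherence rate is wrong. Neither follows. The five-level answers remain in the database if the Annex 3 form is the one captured, the GEE does not use the shell, and the adherence rate in Table 10.2.1 is scored from all six SMAQ answers.

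**Conclusion.** Both shells are wrong as written. This is a reporting defect and should be corrected; it does not touch the primary outcome or any model estimate.

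- **EQ-5D-5L.** If answers are collapsed to fit Table 9.1.1, the proportions improving and worsening are understated in all five dimensions. The certain part is the count in step 1 of the working. The 17% to 65% range for patients rests wholly on assumed distributions and shows only that the effect could be material.
- **SMAQ.** The defect is confined to item-level results. For patients who fail only on item 4, the item table cannot explain their classification as non-adherent.

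**What to change.** 1. Replace Table 9.1.1 and its copies through Table 9.5.3 with five-by-five shift tables plus missing and total, using each dimension's own five response statements from Protocol Annex 3.
2. Add the proportions improved, unchanged and worsened, read from those tables, so that the secondary outcome has an explicit display.
3. Reconcile Protocol 9.3.1 with Annex 3, so that both state five levels.
4. Rebuild Table 10.1.1 on the six Annex 3 SMAQ items: COPD in place of IPF, the weekend item added, the two-daily-doses row removed. All six items are then reportable, against five now.

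The cost is shell and text corrections only. No new data, change of sample size or change of model is needed. The corrections should be made before the tables are programmed.
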